## **10.3 Study Termination**

If LimFlow and/or the ISC and/or principal investigator determine that an event, or event rate presents an unreasonable risk to subjects, then the investigation or parts of the investigation presenting that risk shall be immediately revised or terminated. Termination shall occur not later than 5 working days after the sponsor makes this determination and not later than 15 working days after the sponsor first received notice of the event. LimFlow will notify all participating investigators, and IRBs and the FDA of the termination of the investigation.

# **11.0 Adverse Event Reporting**

## 11.1. General Definitions

An AE is defined as any undesirable clinical occurrence in a subject whether or not it is considered to be device related. In addition, the definition of AE applies to any event with an onset post study procedure or to any underlying diseases, present at baseline that exacerbate in severity post study procedure. Therefore, an underlying disease that was present at the time of enrollment is not reported as an AE, but any increase in the severity of the underlying disease is to be reported as an AE.

The following definitions for rating severity of adverse events will be used:

- Mild: Awareness of signs or symptoms, but easily tolerated; are of minor irritant type; causing no loss of time from normal activities; symptoms would not require medication or a medical evaluation; signs or symptoms are transient.
- Moderate: Interferes with the subject's usual activity and/or requires symptomatic treatment.
- Severe: Symptom(s) causing severe discomfort and significant impact of the subject's usual activity and requires treatment.

A serious adverse event (SAE) is defined as an event which leads to:

- Death due to any cause
- Life-threatening condition
- Results in persistent or significant disability/incapacity
- Requires in-patient hospitalization or prolonged hospitalization
- Necessitates an intervention to prevent a permanent impairment of a body function or permanent damage to a body structure
- Results in congenital abnormality

All SAE's will be reported.

**Device-Related Adverse Event**: an adverse event is considered to be device-related when, in the judgment of the investigator, the clinical event has a reasonable time sequence associated with use of the investigational device and is unlikely to be attributed to concurrent disease or other procedures or medications. It is reasonable to believe that the device directly caused or contributed to the adverse event.

**Procedure-Related Adverse Event**: an adverse event is considered to be procedure-related when, in the judgment of the investigator; it is reasonable to believe that the event is associated with the assigned study procedure and is not specific to the investigational device used. Other products, surgical techniques, or medications required specifically for the procedure are likely to have contributed to the occurrence of the event.

**Concomitant Medication-Related Adverse Event:** an adverse event is considered to be concomitant medication related when, in the judgment of the investigator, it is reasonable to believe that the event is associated with concomitant medications used in conjunction with the investigational device and is not otherwise specific to the investigational device (e.g. bleeding associated with anticoagulation medication).

**Pre-Existing Condition-Related Adverse Event:** an adverse event is considered to be related to a preexisting condition when, in the judgment of the investigator, it is reasonable to believe that the event is associated with the subject's pre-existing condition and is not specific to the investigational device or procedure. Pre-existing conditions that are aggravated or become more severe during or after the procedure should be evaluated on a case-by-case basis to determine if the event may be more appropriately classified as device-related or procedure-related. **Unanticipated Adverse Device Effect (UADE):** Any serious adverse effect on health or safety or any life-threatening problem or death *caused by, or associated with the study device,* if that effect, problem or death was not previously identified in nature, severity, or degree of incidence in the Investigational Plan or any other unanticipated serious problem associated with a device that relates to the rights, safety, or welfare of subjects.

LimFlow, or its designee, in cooperation with the investigator, will assess all adverse events considered to be serious and device-related for potential reportability to the FDA and other regulatory authorities as an Unanticipated Adverse Device Effect (UADE).

The investigator should follow all unresolved serious adverse events until the events are resolved, the subject is lost to follow-up, the subject has withdrawn consent, or the adverse event is otherwise explained.

For purposes of this study, the following events are not considered adverse events, because they are normally expected to occur in conjunction with endovascular procedures / post-procedure, or are associated with customary, standard care of subjects undergoing these procedures:

- Early post-operative pain (within 24 hours post-index procedure) at the access site and/or related to position on procedure table
- Post-anesthesia/conscious sedation emesis, nausea, or headache (within 24 hours postindex procedure)
- Chest pain without associated ECG changes
- Hematocrit decrease from baseline not associated with hemodynamic changes, remaining above 30% and not requiring transfusion
- Electrolyte imbalance without clinical sequelae following endovascular procedure, even if requiring correction
- Low grade temperature increase (≤38.3°C/≤101°F)
- Sinus bradycardia/tachycardia that does not require treatment or intervention
- Systolic or diastolic blood pressure changes that do not require treatment or intervention

This listing of events is intended to provide guidance to the investigational sites for purposes of adverse event reporting. The investigator at the investigational site should utilize his/her own clinical judgment in evaluating adverse experiences, and may decide that the above events should be reported as adverse events.

# **11.2.** Reporting of Serious and Non-Serious Adverse Events

## 11.2.1. General Reporting Requirements (Serious & Non-Serious Adverse Events)

All potentially device- and/or procedure-related adverse events (AE) and all serious adverse events (SAE) will be reported and monitored from the time of treatment through the 6 month follow-up visit. Any SAEs related to the index limb will be reported and monitored throughout the 2 year follow-up visit. The report should include: severity, duration, action taken, treatment outcome and

relationship of the adverse experience to the study device, procedure, concomitant medications, preexisting condition, etc. (i.e., unrelated, related or relationship unknown).

In the case of serious adverse events, procedure and/or device observations and malfunctions, medical record documentation (e.g. procedure notes, operative notes, discharge summary, relevant progress notes, imaging or lab studies) must be provided to sponsor or its designee.

The following criteria must also be adhered to by the investigator in the case of serious adverse events:

- The Adverse Event eCRF must be signed by the investigator.
- It is the responsibility of the investigator to inform their IRB of serious adverse events as required by their IRB procedures and in conformance with FDA and local regulatory requirements.

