## 6.3. Visit Schedule

The study coordinator at the site should schedule the 30-day follow-up visit before the subject is discharged post-procedure. Obtain contact information for subject's significant other or caretaker(s) to ensure that subject will be able to comply with follow-up study visits. Study assessments to be performed at each visit are summarized in Table 1.

TABLE 1: Study Assessment Schedule	Visit 1 Day -1 -21 to -2 (Screen- ing & Baseline)	Visit 2 Day 0 (Treat- ment- dis charge)	Visit 3 30 (+/- 7) Days	Visit 4 60 (+/- 7) Days	Visit 5 (3 mo. +/- 2 wks) & Visit 7 (9 mo. +/- 2 wks)	Visit 6 6 months (+/- 2 weeks)	Visit 8 1 Year (+/- 4 weeks)	Visit 9  2 Year (+/- 4 weeks)
Written Informed Consent	1							
Baseline angiogram/images for screening	1							
Inclusion / Exclusion criteria assessment, including enrollment concurrence by an Independent Safety Committee that subject is not a candidate for conventional surgical or endovascular limb salvage procedures	1							
Demographic data, medical history, medication review, & physical exam	1							
Review of medications / dual anti-platelet regimen 	V	V	$\checkmark$		V	1	1	V
Rutherford Classification (RCC)	1		$\checkmark$		1	V	1	1
Wound healing assessment (completed or not), and photographs 	V		$\checkmark$		1	$\checkmark$	1	V
Index limb oxygenation measurement – TcPO2 	V		$\checkmark$		1	$\checkmark$	1	
Pulse evaluation via continuous wave doppler assessment of grafted area (proximal, graft, and distal to outflow vessels) 	√ (target location)	√8	~		1	V	V	1

TABLE 1: Study Assessment Schedule (cont)	Visit 1 Day -1 -21 to -2 (Screen- ing & Baseline)	Visit 2 Day 0 (Treat- ment- discharge )	Visit 3 30 (+/- 7) Days	Visit 4 60 (+/- 7) Days	Visit 5 (3 mo. +/- 2 wks) & Visit 7 (9 mo. +/- 2 wks)	Visit 6 6 months (+/- 2 weeks)	Visit 8 1 Year (+/- 4 weeks)	Visit 9  2 Year (+/- 4 weeks)
Serum Creatinine	√		$\checkmark$			$\checkmark$		
Numeric Pain Scale Rating (1-10) 	1		1		1	1	1	V
Procedural angiogram and device performance data		V						
Technical Success		4						
Procedural Success		1	1					
Procedure time, defined from sheath insertion to final catheter removal		V						
Fluoroscopy time and Contrast Load for the index procedure		V						
Device- or procedure-related AE/SAE's 		1	V		1	$\checkmark$	1	$\checkmark$

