Assessment of amputation and/or major re- intervention of the Stent Graft			V		V	$\checkmark$	V	V
Duplex Ultrasound Exam to assess Stent Graft patency 			V	1	√9	1		
All-cause mortality			V		1	٦	V	$\checkmark$

 Dual antiplatelet therapy is required for 3 months post-procedure. At a minimum, all subjects must be started on

DAPT at least 1 week before procedure or adequately pre-loaded with DAPT as per institution practice.  Prior to any re-intervention of the stent graft, an angiogram/image and wound photograph should be obtained for adjudication purposes.

TcPO2 will be measured at 2 constant points on the dorsum of the midfoot through the 12 month follow-up.

 Per ACC/AHA 2006 Peripheral Arterial Disease Guidelines

 Review of any hospitalizations or procedures involving the index limb, and/or potentially related to the device or procedure; all SAEs through 6 months. For patients out of area or who refuse to come in for this visit, a telephone

assessment should be conducted to capture as much information as possible at this time point.

 May be performed at any visit as standard of care, as indicated by clinical symptoms.

 Continuous wave doppler must be performed between 4 and 30 hours post-procedure to assess for acute thrombosis; any findings of acute thrombosis must be reported to the Sponsor within 24 hours of the exam. The sponsor must notify the FDA via email of any cases of acute stent graft thrombosis within 5 days of the event.  3 Month visit only

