## 8.2.2.2. Secondary Safety Endpoints Analyses

The secondary safety endpoint will be similarly summarized as described in 8.2.2.1.

Additionally, all serious and non-serious adverse events that are potentially device- and/or procedure-related, and/or related to the index limb will be summarized by type of event, severity, relationship to the device and/or procedure, and timing of event relative to the procedure date.

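### The analysis promises all index-limb adverse events, but the reporting rule omits non-serious ones attributed only to the disease, and all non-serious ones after 6 months

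*Combined protocol and SAP*

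**What the plan says.** **Analysis.** Section 8.2.2.2 states that "all serious and non-serious adverse events that are potentially device- and/or procedure-related, and/or related to the index limb will be summarized". It gives no time limit. The summary is to be broken down by event type, severity, relationship and timing.

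**Definition.** Section 11.1 says of conditions present at enrollment that "any increase in the severity of the underlying disease is to be reported as an AE". It also has a causal category for events where, in the investigator's judgment, "the event is associated with the subject's pre-existing condition and is not specific to the investigational device or procedure".

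**Collection.** Section 11.2.1 requires: "All potentially device- and/or procedure-related adverse events (AE) and all serious adverse events (SAE) will be reported and monitored", and sets the period "from the time of treatment through the 6 month follow-up visit". For the limb it then adds one longer rule: "Any SAEs related to the index limb will be reported and monitored throughout the 2 year follow-up visit".

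**Schedule.** The adverse-event row of Table 1 (Section 6.3) is labelled "Device- or procedure-related AE/SAE's". It is ticked from the treatment visit to 2 years, except at day 60. Its footnote 6 reads: "Review of any hospitalizations or procedures involving the index limb, and/or potentially related to the device or procedure; all SAEs through 6 months".

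**The concern.** The analysis treats a link to the index limb as its own route into the summary, for non-serious events too. The collection rule has no such route. To be reportable, a non-serious limb event must first be judged at least potentially related to the device or procedure.

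That judgment is hard to make in this population. Subjects enter with Rutherford class 5 or 6 disease. The risk list in Section 1.3.1 names edema, infection, lower extremity ischemia, wound dehiscence and wound site pain as possible device or procedure effects, and the disease can produce the same events. The investigator assigns the cause and knows the treatment, because the study has a single arm. For non-serious limb events, that label then decides whether a report is required at all.

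The breakdown by relationship suffers as well. If events judged unrelated are not collected when non-serious, a reader cannot see how many limb events were set aside as disease, or judge whether the attribution was reasonable.

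**Working it through.** No arithmetic applies: the plan states no adverse-event rate and no figure that could be reproduced. The check compares the scope of the analysis with the scope of reporting, one class of index-limb event at a time.

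| Index-limb event | In the 8.2.2.2 summary | Reporting required by 11.2.1 |
|---|---|---|
| Serious, any cause, to 6 months | Yes | Yes |
| Serious, any cause, 6 months to 2 years | Yes | Yes |
| Non-serious, potentially device- or procedure-related, to 6 months | Yes | Yes |
| Non-serious, attributed only to pre-existing disease, to 6 months | Yes | **No** |
| Non-serious, any cause, after 6 months | Yes (no time limit) | **No** |

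Two of the five classes are promised but not required. Other sections might close the gap, so each was checked.

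1. **Section 11.1.** It makes worsening disease reportable without a limit on seriousness or cause. This contradicts 11.2.1 and does not repair it: a site following 11.1 reports the event, and a site following 11.2.1 need not.
2. **Table 1 and footnote 6.** The footnote widens the row to hospital stays and procedures on the index limb and to all serious events up to 6 months. A non-serious, disease-attributed limb event managed without either is still not named. After 6 months the row stays ticked for device- or procedure-related events, although the 11.2.1 window for non-serious events has closed. The two therefore disagree on the last class as well.
3. **Section 6.5.** Visits ask about index-limb complications since the previous visit, but nothing sends the answer to the adverse-event form with a severity and a relationship.
4. **Section 14.2.** Adverse events must be noted in the medical record. A source note is not a report and does not by itself feed the summary.
5. **Section 10.2.** The Independent Safety Committee's ongoing review names serious device- or procedure-related events and device malfunctions or failures. Its adjudication list includes wound healing and index-limb re-interventions, but not the attribution of non-serious events in general.

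None of these gives the two open classes a clear route to the summary.

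**The case against.** The strongest reply is that little would be lost in practice, and several parts of it stand.

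- **Section 11.1 already asks for the report.** This stands in part. A reader might infer that the summary will under-count. The documents do not support that, because some sites may follow 11.1. What they support is that it may under-count and that capture can differ between sites.
- **The missing class is narrow.** This also stands in part. The test is potential relatedness, which is broad, and several common limb events are on the protocol's own risk list. Section 11.1 further asks for individual review of aggravated pre-existing conditions, which may move some into the device- or procedure-related group. Both safeguards still rest on the investigator's judgment.
- **The clinical course is recorded anyway.** This stands. Table 1 schedules Rutherford class, wound status with photographs, and pain at baseline, at 30 days and at 3, 6, 9, 12 and 24 months, whatever the attribution. A reader might infer that a disease-attributed limb event leaves no trace in the data. For a change in Rutherford class or in the wound, that is wrong: what may be missing is the adverse-event entry.
- **The summary is descriptive and the study is a pilot.** True, and it limits the consequence. It does not make the analysis scope and the collection scope agree.

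**Conclusion.** The inconsistency is real. Sections 8.2.2.2 and 11.1 on one side, and 11.2.1 with the Table 1 adverse-event row on the other, define different sets of events. A site that follows 11.2.1 exactly will not supply everything 8.2.2.2 promises. Omission can only lower the total index-limb count, so the error favours the device. Within 6 months it does not change the number of events labelled as related.

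The size cannot be quantified from the documents. A reader might assume that 20% to 40% of the 35 subjects have such an event and conclude that 35 × 0.20 = 7 to 35 × 0.40 = 14 subjects go missing. No figure in the plan supports that rate. The product would also require that none of these subjects is already counted through another index-limb event and that no site acts on 11.1.

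Nor should a reader infer that the main endpoints are biased. Amputation-free survival and limb salvage depend on major amputation and death, which are assessed separately and adjudicated by the Independent Safety Committee.

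The conclusion assumes that Section 11.2.2 (Reporting to Sponsor), whose text was not available to check, does not widen the reporting scope.

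**What to change.** 1. **Section 11.2.1 and the Table 1 adverse-event row:** add that all adverse events of the index limb, serious or non-serious and regardless of attributed cause, are reported through 6 months. This should expressly include worsening of the index wound or of Rutherford class. Keep the 2-year rule for serious index-limb events.
2. **Footnote 6 of Table 1:** say which events are due at the 9-month, 1-year and 2-year visits, so that the ticks agree with 11.2.1.
3. **Section 8.2.2.2:** state the matching window, with non-serious events to 6 months and serious index-limb events to 2 years. Without this step, a 6-month reporting rule would still leave the analysis promising later non-serious events that nobody is required to report.
4. **Section 11.1:** refer to 11.2.1 for what must be reported, so that the definition no longer acts as a second, wider reporting rule.

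The alternative is to narrow 8.2.2.2 to what is now collected and reconcile 11.1 with it. That would be consistent, but it gives up the view of disease-attributed limb events.

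The preferred change costs a few lines of text, slightly more adverse-event entry from visits that already examine the limb, and a higher reported event count.

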## **10.1.2** Post-Procedural Complications

If serious complications or adverse events related to the procedure or device are observed during and through the 6 month follow-up, the events will be individually analyzed for root cause relative to the complete treatment procedure and then evaluated by the Independent Safety Committee and Principal Investigator. The sponsor will assess these events for expedited reporting requirements.

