## **Ongoing Safety Overview:**

The ISC will also review safety data while the study is in progress, including reports of any serious device- or procedure-related adverse events and/or any reports of device malfunction or failure. During the study, the ISC will be asked to ensure that the rights and welfare of the subjects are protected by providing recommendations concerning the continuation, modification, or termination of the study based on review of safety data.

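### Section 11.2.1 ends reporting of device- and procedure-related events at 6 months, apart from index-limb SAEs, while Table 1 collects them to 2 years and 8.2.2.2 tabulates them with no cut-off

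*Combined protocol and SAP*

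**What the plan says.** Section 11.2.1 sets two reporting windows. AEs possibly related to the device or procedure, together with all SAEs, "will be reported and monitored from the time of treatment through the 6 month follow-up visit". The next sentence gives the longer window: "Any SAEs related to the index limb will be reported and monitored throughout the 2 year follow-up visit". It says nothing about other related events after month 6.

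Table 1 in section 6.3 has a row headed "Device- or procedure-related AE/SAE's", ticked at 9 months, 1 year and 2 years as well as earlier. Footnote 6 to that row reads "Review of any hospitalizations or procedures involving the index limb, and/or potentially related to the device or procedure; all SAEs through 6 months". The 6-month limit is attached to the last item only.

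For the analysis, section 8.2.2.2 says that "all serious and non-serious adverse events that are potentially device- and/or procedure-related, and/or related to the index limb will be summarized", with timing from the procedure as one of the classifying factors. It gives no end date.

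Section 11.1 states "All SAE's will be reported", also without a time limit.

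**The concern.** These are stated rules that disagree; the problem is not missing detail. A site working from 11.2.1 would have no instruction to report a related but non-limb event at 9, 12 or 24 months. A site working from Table 1 would record it. The analysis section assumes that such events have been collected throughout.

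What is at stake is how the late safety data are read. Safety is a stated objective, subjects are followed for up to 2 years, and section 10.3 allows an event rate to trigger revision or termination. If the timing table thins out after month 6, a reader could take that as falling risk when part of the drop comes from the reporting rule. Section 1.3.1 lists heart failure and systemic infection among the events that the device or procedure might cause, so late related events outside the limb are foreseen by the protocol.

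**Working it through.** There is no planned figure to reproduce. The check is a comparison of the provisions, followed by a count of visits.

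**Step 1: the rules after month 6**

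| Provision | Related non-serious AEs | Related SAEs outside the limb | Index-limb SAEs |
|---|---|---|---|
| 11.2.1 | not named | not named | reported to 2 years |
| Table 1 AE row | collected at 9, 12, 24 months | collected at 9, 12, 24 months | collected if related |
| Table 1 footnote 6 | reviewed if a hospitalization or procedure is involved | same | same |
| 8.2.2.2 | tabulated, no cut-off | tabulated, no cut-off | tabulated, no cut-off |
| 11.1 | not addressed | reported, no limit | reported, no limit |

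The first two event columns are where 11.2.1 departs from Table 1 and 8.2.2.2.

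**Step 2: remove events that have another route after month 6**

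- Index-limb SAEs: 11.2.1 itself.
- Deaths, acute stent thrombosis and unanticipated adverse device effects: Table 2, with no 6-month limit.
- Major amputations, graft occlusion and index-limb re-interventions: ISC adjudication under 10.2.
- Index-limb procedures and complications: assessed at each visit under 6.5.
- AEs resulting from a device failure or malfunction: recorded on the CRF under 11.3, serious or not.

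Two groups remain after month 6:

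1. non-serious related AEs that do not result from a device failure or malfunction;
2. non-fatal, anticipated related SAEs outside the index limb.

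Group 2 is limited to anticipated events because unanticipated device effects have their own route. Section 11.1 also has the sponsor, with the investigator, assess serious device-related AEs for possible reporting as unanticipated effects. That narrows the group further, but the assessment depends on the event having reached the sponsor.

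**Step 3: how much of the schedule is involved**

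- Visits with the Table 1 AE row ticked: treatment/discharge, 30 days, 3, 6 and 9 months, 1 year, 2 years = 7. The 60-day visit is blank.
- Ticked visits after month 6: 9 months, 1 year, 2 years = 3, and 3/7 = 43%.
- Planned follow-up after month 6: 24 − 6 = 18 months, and 18/24 = 75%.

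These figures describe where the rules differ. They are not counts of lost events.

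**Step 4: section 10.1.2**

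The root-cause and ISC evaluation there applies "If serious complications or adverse events related to the procedure or device are observed during and through the 6 month follow-up". This is the same limit as in 11.2.1, so the two agree. It matters only because it would have to move if 11.2.1 moves. The ISC's ongoing overview in 10.2, "including reports of any serious device- or procedure-related adverse events and/or any reports of device malfunction or failure", carries no time limit.

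**The case against.** The best defence is that 11.2.1 can be read as a minimum. It does not forbid reporting other related events after month 6, Table 1 schedules their collection, and section 15.2.1 obliges investigators to comply with all required elements of the protocol. On that view a site that skipped the Table 1 row would be deviating. A related heart-failure admission at 9 months would fall in the ticked row, in footnote 6, under the general SAE statement in 11.1 and within the ISC's ongoing review. Standardized electronic forms, training and monitoring also make it less likely that sites would diverge.

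Part of this stands. It shows that late related events need not be lost, and that most serious ones have some route. It does not remove the conflict: a general duty to comply does not say which rule governs when two differ. The 11.1 statement conflicts with the 6-month limit on all SAEs in both 11.2.1 and footnote 6, and it does not cover non-serious events.

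A second objection is that 8.2.2.2 is descriptive and plans no comparison of early with late rates. That is correct and limits the consequence to how a table is read.

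Third, section 11.2.2, on reporting to the sponsor, was not in the text reviewed and might settle the matter. That cannot be excluded.

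A reader might go further and estimate the shortfall by assuming that some fraction of sites follow 11.2.1 and the rest follow Table 1. The documents give neither that fraction nor any event rate, so the answer would only restate the assumption.

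**Conclusion.** The inconsistency is real and should be corrected, with limited consequences. For months 6 to 24, and at 3 of the 7 visits where related events are scheduled for collection, 11.2.1 asks for less than Table 1 collects and 8.2.2.2 tabulates. The exposed events are the two groups left in step 2. If sites follow 11.2.1, the timing table could understate them after month 6. The documents do not allow the size of that effect to be estimated.

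Two stronger conclusions might be inferred, and neither is supported. One is that late device safety in general goes uncaptured; the routes in step 2 show otherwise. The other is that the endpoints are compromised. Amputation-free survival (30 days and 6 months) and patency (30 days and 6 months) have their own assessments in Table 1 and fall within the 6-month window, so they are unaffected.

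The conclusion assumes that 11.2.2 does not already extend the reporting period.

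**What to change.** - Amend 11.2.1 so that all AEs and SAEs possibly related to the device or procedure are reported through the 2-year visit, as Table 1 schedules.
- Extend the 6-month limit in 10.1.2 for related serious events to match.
- Keep SAEs that are unrelated and outside the index limb to 6 months, as footnote 6 has it, and qualify the unlimited SAE statement in 11.1 accordingly.
- Check 11.2.2 for consistency with the amended text.

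No visit, scan or test is added. The cost is some additional AE forms and ISC review at the three existing visits after month 6.
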